11.2 Serious Adverse Events

An AE is considered “serious” if in the opinion of the investigator it is one of the following outcomes:

- Fatal
- Life-threatening
- Constitutes a congenital anomaly or birth defect

- A medically significant condition (defined as an event that compromises subject safety or may require medical or surgical intervention to prevent one of the three outcomes above).
- Requires inpatient hospitalization or prolongation of existing hospitalization
- Results in persistent or significant incapacity or substantial disruption to conduct normal life functions.

11.2.1 Reporting of SAEs

All serious and unexpected adverse events should be reported immediately to [name] (page [contact] or her designee [contact])). Only adverse events that the Duke Sponsor-Investigator determines to be serious, unanticipated, and related or possibly/probably (i.e. more likely than not) related to the research must be reported to the Duke IRB. Those adverse events will be submitted in the electronic IRB (eIRB) system, according the following guidelines:

- Report within 24 hours of learning about any subject's death that was unanticipated and more likely related to the research than unrelated;
- Report within 5 business days of learning about any serious, unanticipated, and related or possibly/probably related adverse event;
- Report within 10 business day of learning about any other unanticipated problem or event that was more likely related to the research than unrelated.

11.3 Quality Assurance Program

The Neurosurgery Quality Assurance Program (QAP) ensures adequate oversight for all types of human subject research that are under the Duke Neurosurgery-Clinical Research Unit (NS-CRU) supervision. Oversight begins with an effective scientific and feasibility review process accompanied by a robust data safety and monitoring plan.

The Duke Cancer Institute's Safety Oversight Committee (DCI SOCOMM) in concert with the NS-CRU QAP Monitoring Team (see Section [12.1](#) for Monitoring Team description) oversees the conduct of DUHS cancer-related, sponsor-investigator therapeutic intervention and prevention intervention studies that do not have an external monitoring plan, ensuring subject safety and that the protocol is conducted, recorded and reported in accordance with the protocol, standing operating procedures (SOPs), Good Clinical Practice (GCP), and applicable regulatory requirements.

12 QUALITY CONTROL AND QUALITY ASSURANCE

12.1 Monitoring

This clinical research study will be monitored both internally by the PI and by the Department of Neurosurgery. In terms of internal review, the PI will continuously monitor and tabulate adverse events. Appropriate reporting to the Duke IRB will be made. The PI of this study will also continuously monitor the conduct, data, and safety of this study to ensure that:

- Interim analyses occur as scheduled;
- Stopping rules for toxicity and/or response are met;
- Risk/benefit ratio is not altered to the detriment of the subjects;
- Appropriate internal monitoring of AEs and outcomes is done;
- Over-accrual does not occur;
- Under-accrual is addressed with appropriate amendments or actions;
- Data are being appropriately collected in a reasonably timely manner.

The data and safety monitoring responsibilities are shared amongst Investigators, Neurosurgery Oversight Team, Neurosurgery Research Working Group and Duke Research Compliance Assurance (RCA) team.

The studies that are higher-risk (risk level II, III and IV), prospective studies that consent subjects will be subjected to internal reviews. The following table (table: 1) describes the risk levels for the studies:

	Risk Level I	Risk Level II	Risk Level III	Risk Level IV
Study funding source	Investigator Initiated Trial	Investigator Initiated Trial	Investigator Initiated Trial	Investigator Initiated Trial
Trial design	Retrospective chart reviews Exempt data/tissue collection	• Prospective - Specimen and data collection studies • Single Arm study - off label use of approved drug/device	• Single Arm study – Multiple IND drug regimen • Multiple arms (cohorts or treatments) – No Randomization • Multiple arms – simple randomization ph II or I/II studies	Multiple arms - with Randomization – single or double blinding
Complexity of the study regimen	No drug or device involved	FDA approved drug/ Device Non-Significant Risk Device	• Single drug/ IND study • Multiple drug/ IND study • IDE device study • IND + Device combination study	• Single drug/ IND study • Multiple drug/ IND study • IDE device study • IND + Device combination study
Toxicity profile/Subject risk profile	Low to No toxicity profile	Known toxicity profile	Potentially significant toxicity profile	Expected high toxicity profile

Table 1: Different Risk Levels for Investigator Initiated Trials

The study risk assessment is done by the PI and the study team during the protocol development process. The expectation is that all Investigator Initiated perspective interventional studies have a monitoring plan written in the protocol. This monitoring plan will be reviewed and approved by the scientific reviewers during the scientific review of the study.

Other types of studies that might be subjected to internal reviews are listed below:

- Studies being conducted by a new PI or a new study staff or both;
- Sponsored interventional studies for which Duke NSCRU is amongst the highest enrolling sites;
- Any phase III interventional studies that are close to receiving an FDA approval for the IND/IDE it is testing.

Any study that does not fall under the above mentioned criteria are low-risk studies (e.g., retrospective chart reviews). Those studies may be monitored only for data integrity, completeness and/or maintenance of all applicable regulatory approvals.

This study falls under the Risk Level III category. This means that this study is more interventional in nature and may require a higher scrutiny. The studies that fall into this category will have the following oversight:

- Review of the subject chart and 100 % of the data of the first 2 subjects enrolled.
- Review of the Regulatory binder after the first 2 subjects are enrolled.
- Drug/Device accountability logs after the first 2 subjects are enrolled and have received a study intervention.
- Ongoing reviews will be done quarterly until the study is closed to enrollment and subjects are no longer receiving study interventions that are more than minimal risk, and will include:
 - Review of the informed consents of all subjects enrolled
 - Subject charts, drug/device accountability and specimen collection process of 20 % of the subjects enrolled on the study
 - Review of any major deviations or safety events
 - Review of the enrollment status
- Ongoing reviews of the regulatory binders will be performed annually.

Additional monitoring may be prompted by findings from monitoring visits, unexpected frequency of serious and/or unexpected toxicities, or other concerns and may be initiated upon request of the NS-CRU QAP, DUHS and DCI leadership, the DCI Cancer Protocol Committee (CPC), the SOCOMM, the sponsor, the Principal Investigator, or the IRB. All study documents must be made available upon request to the QAP Monitoring Team and other authorized regulatory authorities, including but not limited to the National Institute of Health, National Cancer Institute, and the FDA. Every reasonable effort will be made to maintain confidentiality during study monitoring.

12.2 Audits

The Duke Office of Audit, Risk and Compliance (OARC) may conduct audits to evaluate compliance with the protocol and the principles of GCP. The PI agrees to allow the OARC auditor(s) direct access to all relevant documents and to allocate his/her time and the time of the study team to the OARC auditor(s) in order to discuss findings and any relevant issues.

OARC audits are designed to protect the rights and well-being of human research subjects. OARC audits may be routine or directed (for cause). Routine audits are selected based upon risk metrics generally geared towards high subject enrollment, studies with limited oversight or monitoring, Investigator initiated Investigational Drugs or Devices, federally-funded studies, high degree of risk (based upon adverse events, type of study, or vulnerable populations), Phase I studies, or studies that involve Medicare populations. Directed audits occur at the directive of the IRB or an authorized Institutional Official.

OARC audits examine research studies/clinical trials methodology, processes and systems to assess whether the research is conducted according to the protocol approved by the DUHS IRB. The primary purpose of the audit/review is to verify that the standards for safety of human subjects in clinical trials and the quality of data produced by the clinical trial research are met. The audit/review will serve as a quality assurance measure, internal to the institution. Additional goals of such audits are to detect both random and systemic errors occurring during the conduct of clinical research and to emphasize “best practices” in the research/clinical trials environment.

12.3 Data Management and Processing

12.3.1 Study Documentation

Study documentation includes but is not limited to source documents, case report forms, monitoring logs, appointment schedules, drug calendars, study team correspondence with sponsors or regulatory bodies/committees, and regulatory documents that can be found in the “Regulatory Binder,” which includes but is not limited to continuing reviews, safety events, and amendments, approved and signed informed consent forms, and College of American Pathologists (CAP), Commission on Office Laboratory Accreditation (COLA), and Clinical Laboratory Improvement Act (CLIA) laboratory certifications.

Source documents are original records that contain source data, which is all information in original records of clinical findings, observations, or other activities in a clinical trial necessary for the reconstruction and evaluation of the trial. Source documents include but are not limited to hospital records, clinical and office charts, laboratory notes, memoranda, subjects’ diaries, drug calendars or evaluation checklists, pharmacy dispensing records, recorded data from automated instruments, copies or transcriptions certified after verification as being accurate copies, microfiches, photographic negatives, microfilm or magnetic media, x-rays, subject files, and records kept at the pharmacy, at the laboratories and at medico-technical departments involved in the clinical trial. When possible, the original record should be retained as the source document. However, a photocopy is acceptable provided that it is a clear, legible, and an exact duplication of the original document.

12.3.2 Case Report Forms

Paper Case Report Forms (CRFs) will be created for purposes of eligibility and data collection. The information from the paper CRFs will then be entered into the eCRF in REDCap™.

The eCRF will be the primary data collection document for the study and is developed in conjunction with statistical oversight. The eCRFs will be updated in a timely manner following acquisition of new source data. Only study personnel trained for accessing and entering data in REDCap™ are permitted to make entries, changes, or corrections in the eCRF.

An audit trail will be maintained automatically by the electronic CRF management system, REDCap™. All users of this system will complete user training, as required or appropriate per institutional requirements and other regulations.

12.3.3 Data Management Procedures and Data Verification

Access to electronic databases will be managed by the Data Manager.

Completeness of entered data will be checked automatically by the eCRF system, and users will be alerted to the presence of data inconsistencies. Additionally, the data management team and the statistical team will cross-reference the data to verify accuracy. Missing or implausible data will be brought to the attention of the PI requiring appropriate responses (i.e. confirmation of data, correction of data, completion or confirmation that data is not available, etc.).

The database will be reviewed and discussed prior to database closure, and will be closed only after resolution of all remaining queries. An audit trail will be kept of all subsequent changes to the data.

12.3.4 Coding

All medical terms will be coded using CTCAE v.4.

12.3.5 Study Closure

Following completion of the studies, the PI will be responsible for ensuring the following activities:

- Data clarification and/or resolution;
- Review of site study records for completeness.

13 STATISTICAL METHODS AND DATA ANALYSIS

All statistical analysis will be performed under the direction of the statistician designated in key personnel. Any data analysis carried out independently by the investigator must be approved by the statistician before publication or presentation.

13.1 Analysis Sets

All evaluable subjects will be included in efficacy and safety analyses.

13.2 Patient Demographics and Other Baseline Characteristics

Socio-demographic and clinical characteristics of patients enrolled onto this study will be summarized. For categorical variables, frequencies and percentages will be provided. Means with standard deviations and medians/percentiles will summarize non-categorical variables.

13.3 Treatments

The number of patients treated on each arm (LCM, LEV, or no AED) will be calculated.

13.4 Primary Objectives

The primary objective of this study is to assess the impact of LCM, LEV or, no AED in patients undergoing MSR for suspected new, recurrent or transformed glioma (WHO Gr I-IV) or brain metastasis. The basis for making this assessment will be the number of ED visits or readmissions within 30 days of MSR.

13.4.1 Variables

Percentage of subjects with an emergency room visit or re-hospitalization within 30 days after MSR.

13.4.2 Statistical Hypothesis, Model, and Method of Analysis

Though the percentage of patients who are re-hospitalized or have an emergency room visit during the 30 days post-MSR will be calculated within each treatment group, the primary comparison will combine outcome observed within the LCM and LEV arms. The statistical comparison will assess the impact of AED (LCM or LEV) relative to no AED on this endpoint.

Let us define P1 and P2 as follows:

P1 = Percentage of patients treated prophylactically with AED (LCM or LEV) who are re-hospitalized or have an emergency room visit during the 30 days post-MSR

P2 = Percentage of patients not prophylactically treated (i.e. no AED) who are re-hospitalized or have an emergency room visit during the 30 days post-MSR

Given that current guidelines recommend against peri-operative seizure prophylaxis, we are interested in showing that AED is better than No AED, or $P1 < P2$, or $0 < P2 - P1$. Hence, the hypothesis we will be testing is:

$$H_0: \theta \leq 0 \text{ vs } H_1: \theta > 0$$

where $\theta = P2 - P1$. A one-tailed test using a large-sample Z test will be conducted given the directional hypothesis that is being posed.

With stratification for suspected grade (LGG vs HGG), the Cochran-Mantel-Haenszel test statistic will compare patients who do and do not receive AED with respect to the proportion of patients re-hospitalized or have an emergency room visit during the 30 days post-MSR.

An interim analysis will be conducted half way through the study to assess whether early study termination is appropriate. An O'Brien-Fleming boundary will provide guidance for making that assessment. This interim analysis will determine whether the hypothesis can be rejected or accepted at that time. See section 13.7 and 13.8 for further detail.

An intent-to-treat philosophy will be used in generating statistical analyses.

13.4.3 Handling of missing values, censoring, and discontinuations

Given that the length of follow-up required after brain surgery is limited to 30 days in terms of data collection, we anticipate there being a minimal amount of missing primary outcome data.

In the event that a patient does not complete the 30 day follow-up due to death, the patient will be treated as if they were either re-hospitalized and/or visited the emergency room.

If a subject withdraws study participation between randomization and the MSR, that subject will be excluded from primary analyses. An additional patient will be randomized to the study to replace that subject to meet the

sample size requirements for the study. It is not believed that the knowledge of treatment group assignment would influence a patient's decision to withdraw from the study.

13.5 Secondary objectives

This study has one secondary objective which is to assess the safety and tolerability of LCM and LEV.

Adverse events will be assessed according to the NCI Common Toxicity Criteria for Adverse Events (CTCAE) version 4. For each type of toxicity, the maximum grade experienced by the patient will be summarized with frequency distributions based upon all AESIs. Of particular interest are those adverse events of special interest (AESI), as defined in section [7.1.4](#), that occur within 30 days after MSR.

The percentage of patients experiencing any grade adverse events of special interest within 30 days of MSR will be summarized in each of the 3 treatment arms, and compared using chi-square tests. If AED is shown to have fewer re-hospitalizations or ED visits, then a pairwise comparison of LCM and LEV is of particular interest.

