5.2.9 Study Purpose and Rationale

The primary purpose of this study is to evaluate 30-day readmission rates and ED visits through randomizing subjects to "no AED" or to the 2 primary AEDs used in this patient population here at DUMC.

Current guidelines recommend against peri-operative seizure prophylaxis for patients with newly diagnosed brain tumors; however, they were based on older generation AEDs that were associated with severe toxicities and drug-drug interactions. In light of newer generation AEDs with more tolerable safety profiles, some neurosurgeons and neuro-oncologists prescribe AEDs to patients for prolonged periods of time after surgery, despite these guidelines; this has also been the practice here at DUMC. Given the lack of recommendation for AED prophylaxis in the peri-operative period by the neurosurgical guidelines, which is contrary to Duke's practice, and given the cost and potential side effects of AEDs, it was determined that it is now time to formally assess the impact and side effect profile of the use or not of AEDs. If determined that AED is necessary, this study will also attempt to evaluate the side effect profile of the commonly used AED at Duke (levetiracetam) versus a newer AED (lacosamide).

The question most relevant to Duke neurosurgeons is the rate of readmission and ED visits after a Maximum Safe Resection (MSR) (gross-total, sub-total or biopsy), a measurable patient outcome to their surgery. If there is benefit on these rates from having an AED, that would provide support for neurosurgeons to prescribe AEDs. If there is no difference in readmission rates/ED visits between those who did and did not receive an AED, then there would be much more support against AED prophylaxis. If the adverse side effects of the AEDs studied are significant, then there will be a greater consideration of risk to benefit.

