13.8 Sample Size

Eligible subjects will be randomized to one of 3 treatment arms (LCM, LEV, or no AED) using an allocation ratio of 1:1:2. Randomization will be implemented using a permuted block algorithm. Randomization will be stratified by suspected grade of glioma (high vs low grade) or brain metastasis..

The experience of subjects in the LCM and LEV groups will be combined to estimate the percentage of subjects with an ED visit or readmission within 30 days of MSR after seizure prophylaxis pre-surgery. That outcome will be compared to the same outcome observed among patients in the no AED group.

In designing this study, we have considered the following background information:

- In a recently conducted retrospective review of Duke’s experience with AEDs and MSR (Pro00047350 Descriptive and Cost Analysis of Post-procedure Anti-Epileptic Drugs in Malignant Glioma), the experience of patients newly diagnosed with malignant glioma and without prior seizure history or AED use was examined. Among those patients who were prophylactically treated with LEV before MSR, 12% of subjects were re-hospitalized or visited emergency room within 30 days post-MSR.
- Published literature indicates that the risk of post-MSR seizure in MG patients without AED prophylaxis ranges from 2.3% up to 35%, particularly in glioblastoma (GBM).^{75,77,78}

Therefore in designing the study we have assumed that the percentage of patients with re-hospitalization or ED visits within 30 days post-MSR is 12% in both the LCM and LEV groups. We have also designed the study to detect an increase in re-hospitalization or ED visits to 25% within the no AED group.

Additional assumptions for the power calculations include the following:

- One-tailed test conducted so that the overall type I error rate is 0.05. This type I error rate accounts for one interim analysis.
- Power = 80% under the alternative where the true outcome is 12% in the AE group (combined) and 25% in the no AED group.
- One interim analysis half way through the study that allows early termination with either acceptance or rejection of the null hypothesis.

Under these conditions, there is a need to randomize and follow 232 subjects for 30 days. An interim analysis as described in Section [13.7](#) will be conducted after 116 patients (SAS PROC SEQDESIGN).

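### Protocol 13.5 compares adverse events of special interest by chi-square with no risk difference or confidence interval, so a non-significant LCM–LEV result could be read as similar tolerability when a 15-point difference would often be missed

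*Protocol*

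**What the plan says.** Protocol 13.5 names one secondary objective, the safety and tolerability of LCM and LEV. (SAP Section 3 lists it first of six.) The percentages of patients with any-grade AESIs within 30 days of MSR "will be summarized in each of the 3 treatment arms, and compared using chi-square tests". The section adds: "If AED is shown to have fewer re-hospitalizations or ED visits, then a pairwise comparison of LCM and LEV is of particular interest". For each toxicity, "the maximum grade experienced by the patient will be summarized with frequency distributions". No risk difference, interval, margin, significance level, sidedness or power is given for these comparisons.

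Protocol 5.2.9 explains how side effects enter the overall judgement: "If the adverse side effects of the AEDs studied are significant, then there will be a greater consideration of risk to benefit". It attaches no test or threshold to the word significant. The same section gives comparing the side-effect profiles of LEV and LCM as an aim if an AED proves necessary.

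Protocol 13.8 sizes the trial on the primary endpoint alone: "there is a need to randomize and follow 232 subjects for 30 days", with arms allocated "using an allocation ratio of 1:1:2". Section 13.7 plans one interim analysis after 116 patients.

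The SAP text available ends in its variable definitions, before any analysis methods. What follows about missing intervals therefore applies to the protocol only.

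**The concern.** A chi-square test answers whether the observed difference is hard to explain by chance. It does not say how large an excess of harm the data still allow, and that is what a tolerability conclusion needs. When the test is the only stated between-arm inference, a non-significant result is easily reported as no difference. Section 5.2.9 is open to that habit: it leaves significant undefined for side effects, and on the primary endpoint it treats the absence of a difference as support for one conclusion.

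The comparison most exposed is LCM against LEV. It uses only half the patients, and 13.5 gives it special interest when AED beats no AED. If that happens at the interim, it must be made on about half the planned arm sizes.

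**Working it through.** **Inputs from the documents.** N = 232, interim at 116, allocation 1:1:2 (13.7, 13.8). At full accrual the arms are 58 LCM, 58 LEV and 116 no AED; at the interim, 29, 29 and 58. Primary design: 12% vs 25%, one-sided 5%, 80% power, interim boundaries 0.48887 and 2.31015, final boundary 1.63351.

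**Assumptions, not in the documents.** AESI test two-sided at 5%, without continuity correction; a true difference of 15 points; lower-arm AESI rate from 10% to 50%. The nearest anchors are a 10% AE rate on LEV 500 mg BID (5.2.8), and behavioural AEs on LEV of about 13%, up to 30% for some (5.2.5). The composite in 7.1.4 counts any grade of 15 event types, so a rate below 10% looks unlikely.

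**The plan's own figure first.** A two-stage calculation with the stated boundaries and unpooled variance gives type I error 0.0500 and power 80.3% at N = 232. Exactly 80% needs N = 230 (237 with pooled variance). The stated 232 is reproduced.

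**Chance of stopping for benefit at the interim**, under 12% vs 25% with 58 vs 58:
- SE = √[(0.12×0.88 + 0.25×0.75)/58] = 0.0711
- Expected Z = 0.13/0.0711 = 1.83
- P(Z > 2.31) = 1 − Φ(0.48) ≈ 0.315

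Exact binomial versions give 0.301 (pooled) and 0.320 (unpooled), so about 30%. Under the null it is about 1%.

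**Miss rate for a 15-point difference.** Miss = 1 − Σ Bin(x₁; n₁, p₁) Bin(x₂; n₂, p₂) over all tables where the Pearson chi-square is significant at 5%. A hand check by normal approximation, 10% vs 25% at 58 vs 58:
- pooled rate 0.175; SE₀ = √(2×0.175×0.825/58) = 0.0706
- SE₁ = √[(0.10×0.90 + 0.25×0.75)/58] = 0.0692
- power = Φ[(0.15 − 1.96×0.0706)/0.0692] ≈ Φ(0.17) = 0.567, so miss = 0.433 (exact 0.414)

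| Comparison | n | Missed, lower rate 10–50% |
|---|---|---|
| LCM vs LEV, full accrual | 58 vs 58 | 41–63% |
| LCM vs LEV, interim stop | 29 vs 29 | 68–80% |
| One drug vs no AED, full accrual | 58 vs 116 | 27–54% |
| One drug vs no AED, interim stop | 29 vs 58 | 53–72% |
| Pooled AED vs no AED, full accrual | 116 vs 116 | 13–35% |
| Pooled AED vs no AED, interim stop | 58 vs 58 | 41–63% |

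A single three-arm test (2 df) at 58/58/116 with the excess on one drug misses 30–59% by simulation.

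**Sensitivity of the LCM–LEV figures.** With a Yates correction: 53–70% (58 vs 58) and 80–86% (29 vs 29). With a one-sided 5% test at 58 vs 58: 31–51% (normal approximation). At a 5% lower rate: 28% and 56%. For 80% power at 15 points, about 100 per arm (10% vs 25%) to 174 per arm (42.5% vs 57.5%) would be needed.

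**Interval width when observed rates are equal.** Half-width = 1.96√[p(1−p)(1/n₁ + 1/n₂)]. At 58 vs 58: 1.96√(0.09×2/58) = 0.109 for p = 0.10 and 1.96√(0.25×2/58) = 0.182 for p = 0.50. At 29 vs 29: 0.154 to 0.257. At 116 vs 116: 0.077 to 0.129.

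**The case against.** The strongest reply is that this is about reporting. Secondary endpoints are often unpowered, the protocol nowhere says that a non-significant AESI test means equal safety, and intervals can be computed from the reported counts. Section 13.5 also plans percentages by arm and maximum-grade tables, so it offers more than a test result. All of that is true. But percentages and grade tables carry no statement of uncertainty, and leaving intervals to be derived later means the safety conclusion has no pre-specified basis other than the test.

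Two stronger readings are tempting and not supported. A reader might infer that the AED risk-benefit decision turns on the chi-square p-value. Section 5.2.9 is background rationale, names no test, and promises only closer consideration; significant may mean clinically significant. A reader might also attach the 41–63% figure to AED against no AED. At full accrual that figure belongs to LCM against LEV. The use-or-not question rests on 116 vs 116 pooled, or 58 vs 116 per drug, where the miss rates are lower. Section 13.5 does not itself ask for the pooled AESI contrast.

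The 29 vs 29 case is close to a floor: no accrual pause is stated while the 116 patients complete follow-up, and 13.7 calls its boundaries guidelines.

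**Conclusion.** The point holds in limited form. Protocol 13.5 gives chi-square tests as the only stated between-arm inference for AESIs, with no measure of precision, and 5.2.9 leaves significant undefined. A non-significant result would be weak evidence of similar tolerability, above all for LCM against LEV: a 15-point difference is missed 41–63% of the time at full size and 68–80% at about 29 vs 29. That smaller size arises with about 30% probability under the design alternative. Even with identical observed rates, the 95% interval for LCM minus LEV would reach about ±11 to 18 points, or ±15 to 26 after an early stop. AED against no AED is better placed (27–54% per drug, 13–35% pooled).

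These sizes rest on the assumed test, difference and base rate set out above. The primary design is unaffected, and nothing is claimed about the SAP's analysis methods.

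**What to change.** In 13.5, make three AESI risk differences the basis for the safety conclusion: LCM minus LEV, LCM minus no AED, and LEV minus no AED. Give each a two-sided 95% confidence interval (Newcombe, for example), and keep the chi-square tests as supportive.

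Report each difference twice: for the full composite and for AESIs excluding seizure. Section 7.1.4 counts seizure of any grade as an AESI. An AED that prevents seizures could therefore offset its own toxicity in the composite against no AED. The AESI list in SAP Section 7 already leaves seizure out and holds it as a separate outcome.

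State that a non-significant difference will not be taken as evidence of equal safety or of no added harm. In 5.2.9, replace the undefined word significant with a reference to the estimated excess and its upper confidence limit. If the trial stops at the interim, give the intervals at the arm sizes actually reached and label the LCM–LEV safety comparison as imprecise.

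The cost is a few sentences in 13.5 and 5.2.9, matching text in the SAP, and one table from data already collected. No patients or procedures are added. The downside is that wide intervals will visibly limit tolerability claims, especially for LCM against LEV after an early stop.
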